Therapeutic plasma exchange (TPE) offers an immediate and scientifically grounded intervention for the removal of a host of pathogenic antibodies and toxic molecules by centrifugal separation of plasma or plasma membrane filtration. Xiao⁵ and colleagues successfully incorporated TPE in the management of a patient with severe CRS following CAR-T treatment in conjunction with Tocilizumab and steroids with daily documentation of cytokine levels.

Precedence for consideration of TPE in a variety of inflammatory dominant disease states is well known. Interest in adjuvant treatment for management of sepsis and multi organ dysfunction is reflected in Busund⁶ and Rimmer⁷ manuscripts. Patel et al⁸ successfully used TPE in three pediatric patients with pH1N1 influenza A acute respiratory failure and hemodynamic shock despite failure of best supportive care. All three survived with “good functional recovery.”

Ruxolitinib is a JAK/STAT pathway inhibitor which is FDA approved for polycythemia rubra vera, myelofibrosis and graft versus host disease. Kenderion et al⁹ reported a murine model of CRS following CAR-T cellular therapy with marked elevation of IL-6, interferon-gamma, TNF alpha mimicking human CAR-T therapy induced CRS. Ruxolitinib treated mice demonstrated clinical amelioration and decrement in inflammatory cytokines. Incyte Corporation has announced plans to launch a Phase III trial of single agent ruxolitinib for COVID-19 associated cytokine storm.

This protocol will evaluate the efficacy of TPE alone or in combination with ruxolitinib in COVID positive patients with PENN grade 2, 3, 4 CRS. It is hypothesized that dual intervention of acute aphaeretic depletion of cytokines and concomitant suppression of production will produce superior amelioration of the cytokine load and to help to prevent cytokine load rebound. This protocol is envisioned as a pilot study (n=20) for hypothesis generation for future investigation.

Primary Endpoints

1. To document the efficacy of TPE alone or in conjunction with ruxolitinib in decreasing the cytokine load over a 14-day intervention study
2. Analysis of all therapy related adverse events (AEs)

Secondary Endpoints

1. To correlate the clinical course of participants with the degree of specific cytokine reductions
3. To calculate time to independence from mechanical ventilation
4. To calculate time to independence from supplemental oxygen therapy
5. To measure CRP, ferritin and cytokine levels (IL-6, IL-8, IL-10, TNF α , IFN γ , GM-CSF) to map the cytokine landscape over the course of the study
6. To explore correlative biomarker studies
7. To bank plasma and other blood derivatives in the Prisma Health ITOR Biorepository for future investigation

Study Design

Study type:	Interventional Pilot Clinical Trial
Estimated Enrollment	20 patients
Allocation	Two sequential cohorts, 10 patients per cohort First 10 patients will receive TPE alone (Cohort 1A) Second 10 patients will receive TPE in combination with ruxolitinib
Masking	None (open label)
Primary purpose	Treatment efficacy
Official title:	Interventional Study to Evaluate the Efficacy of Therapeutic Plasma Exchange (TPE) Alone or in Combination with Ruxolitinib in COVID-19 Positive Patients with PENN Grade 2, 3, 4 Cytokine Released Syndrome (CRS)

Study Population

COVID-19 positive patients with PENN grade 2, 3, 4 CRS and respiratory failure.

Eligibility

Inclusion:

1. Patients positive for COVID-19 by PCR or alternative accepted methodology
2. PENN class 2,3,4 CRS¹⁰
3. Respiratory insufficiency with supplemental oxygen to maintain O2 sat greater than 89%
4. Clinically positive imaging by CXR or CT scan with evidence of bilateral pulmonary infiltrates, ground glass opacification or other pattern of consolidation felt likely to be linked to COVID infection or complication thereof
5. Adults 22 years of age or older

Exclusion:

1. Pregnancy
2. Breast feeding
3. Class 3-4 NYHA heart failure
4. Current use of synthetic disease modifying anti-rheumatic drugs (DMARDs), with the exception of hydroxychloroquine, or IL-6 inhibitors or other immunosuppressive therapies outside of number five below
5. Current use of chronic corticosteroids if in excess of prednisone 10mg per day or equivalent
6. Suspected or confirmed clinically significant bacterial infection
7. History of TB
8. History of HIV
9. History of IBD
10. JAK inhibitor use within last 30 days
11. Creatinine clearance less than 15 ml / min
12. Absolute neutrophil count < 1000
13. Platelet count < 50,000
14. AST or ALT > 5 times the upper limit of normal
15. Clinical assessment that TPE or ruxolitinib could pose unacceptable risk by study participation or the treatment is deemed inappropriate by a study investigator
16. Current enrollment on another investigational protocol for COVID-19 induced CRS
17. Stage 4 obstructive lung disease with chronic hypoxic respiratory failure requiring supplemental O2 at baseline, or ILD with chronic hypoxic respiratory failure requiring supplemental O2 at baseline

Treatment Plan

Device: Spectra Optia Apheresis System

Intended Use of Device: Therapeutic Plasma Exchange performed per marketed labeling

Drug: Ruxolitinib (generic) marketed as brand name, Jakafi ,manufactured by Incyte Corporation, will be used per the marketed package insert.

Cohort 1A: TPE, five single plasma volume exchanges over 7 days (every day x 2 then every other day x 3) with albumin or FFP replacement if underlying coagulopathy per institutional protocol (Appendix A).

Other – standard medical care

Cohort 1B: TPE as in cohort 1A combined with ruxolitinib 5mg po BID beginning day prior to first TPE and continuing BID for total of 14 days. On days of TPE, ruxolitinib dosing will be immediately post procedure and a second dose approximately 8 hours later.

Other – standard medical care

Schedule of Assessments

Pre Treatment

Standard of Care Assessments

- Complete Blood Count (CBC)
- Comprehensive Metabolic Panel (CMP)
- C-Reactive Protein (CRP)
- Ferritin
- lipid panel
- Hepatitis B Surface Antigen, Hepatitis B Surface Antibody, Hepatitis B Core Antibody and Hepatitis C Antibody
- PT/INR
- Partial Thromboplastin Time (PTT)
- Fibrinogen
- type and screen
- serum pregnancy test
- physical examination

Study Related Assessments

- cytokine panel
- peripheral blood for biorepository
- peripheral blood for pharmacogenomics

During Treatment (On Study)

Standard of Care Assessments

- daily CBC
- daily CRP
- PaO₂/FiO₂ ratios days (with ABGs) per Appendix B
- amount of supplemental O₂, SPO₂%, respiratory rate, imaging per MD discretion (*for non-intubated patients*)
- measure daily SPO₂%, FiO₂; PEEP; and lung compliance (inspiratory pause – V_t/P_{plat} – PEEP) or plateau pressures (*mechanically vented patients*)
- daily Basic Metabolic Panel (BMP)
- physical examination

Study Related Assessments

- daily collection of study related adverse events and/or serious adverse events
- Fibrinogen (on days of TPE only)
- daily cytokine panel and GM-CSF
- repeat cytokine panel and GM-CSF within 60 minutes post TPE (on days of procedure only)
- serum ferritin per Appendix B
- peripheral blood and plasma waste for biorepository per Appendix B
- day 28 office visit or virtual health visit to assess clinical status of the patient

Risk Analysis

The proposed patient population is not anticipated to be at an increased risk compared to a clinically similar population without COVID-19 infection. The device and drug will be used as marketed. Standard risks for the device and drug are outlined in the patient informed consent document. Risks will be minimized by conducting the trial in the inpatient setting of an acute care hospital with dedicated and trained therapeutic apheresis staff, licensed medical personnel and experienced research team members under the direction and oversight of the principal investigator. In the event of patient status improvement, discharge will be acceptable after completion of therapeutic plasma exchange. Daily outpatient follow-up through patient completion of study required assessments will occur in a dedicated phase I research unit.

Removal of medications with TPE is a risk. However, consultation with a hospital pharmacist will occur as needed to determine if a change in timing of medication administration is needed or if medication reloading should occur post TPE.

Dose Modifications

The starting dose of ruxolitinib is 5mg po bid. The need for dose adjustments will be assessed on a daily basis by the research team and pharmacist.

- AST/ALT > 5x ULN, reduce dose of ruxolitinib to 5mg po once daily¹¹
- Platelet count between 25,000 and 35,000, reduce dose of ruxolitinib to 5mg po once daily. Platelet count < 25,000, hold ruxolitinib. May resume once platelet count >25,000 with dosing based on actual platelet count.
- Absolute neutrophil count < 500, hold ruxolitinib until > 500 then resume at full dose
- Creatinine Clearance <15ml/min, discontinue ruxolitinib

Duration of Investigations

A six month patient recruitment period is anticipated. Patient participation is 15 days in duration. An additional six month period of data analysis is anticipated for an overall period of investigation equaling 12 months

Treatment Discontinuation

Treatment discontinuation will occur under the following conditions:

- The patient withdraws consent either from treatment or from the study
- The patient is lost to follow-up
- The patient experiences a side effect that per the protocol requires treatment to end
- The physician deems treatment discontinuation is in the best interest of the patient
- The patient is found to be eligible to participate in the study after being enrolled and continued treatment in this study is not in the best interest of the patient
- The patient is found to be pregnant or intends to become pregnant
- The patient is noncompliant with the study requirements your disease worsens

Data Handling and Recordkeeping

The principal investigator will carefully monitor study procedures to protect the safety of research subjects, the quality of data, and the integrity of the study. All study subject material will be assigned a unique identifying code or number. The key to the code will be kept in a locked file in the Research Division of the Prisma Health Cancer Institute.

Data Collection, Analysis and Outcomes

REDCap EDC software will be used for data management and future statistical analysis. Designated Cancer Institute research staff will perform extraction of patient records.

Overall Response Rate (ORR) will be defined as $\geq 33\%$ decrease in the cytokine load from peak value through study day 14 in one-third or more participants.

Ethical Considerations

This study will be conducted in accordance will all applicable government regulations and Prisma Health research policies and procedures. This protocol and any amendments will be

submitted and approved by the Prisma Health Institutional Review Board (IRB) prior to any study activity.

All study participants will provide informed consent allowing for their tissue and de-identified clinical information to be used for research purposes.

Safety Monitoring and Reporting

A Drug Safety Monitoring Board (DSMB) will be established consisting of a hematologist, pulmonologist and infectious disease specialist not associated with the research team for this investigation. The committee will review all serious adverse events within 48 hours and will review all patient outcomes for cohort 1a before proceeding to enrollment of cohort 1b.

Adverse Events

Adverse events (AEs) are defined as an unexpected medical problem that happens during treatment with a drug or other therapy. The NCI Common terminology criteria for adverse events (CTCAE Version 5.0) will be used as the standardized severity grading system. AEs will also be reported by degree of relatedness as not related, possibly related, likely related or related to the study drug or study therapy.

SAE Reporting to Incyte

The Principal Investigator (PI) must report all Serious Adverse Events (SAEs) to Incyte within 24 hours of learning of an event, regardless of the PI's causality assessment. This notification will be provided on a completed Serious Adverse Event (SAE) form. SAE reporting for each subject begins the day the informed consent is signed by the patient and within 30 days after subject has completed or discontinued from the study or has taken last dose of the study drug, or as described in the protocol.

SAEs, occurring using Incyte study drug, are reported in accordance with the effective protocol. SAEs occurring with any other commercial drug are reported to the manufacturer of that drug in accordance with regulations and protocol.

Initial SAEs and/or subsequent follow-up reports will be reported via email to [contact] or fax (+) [name]. SAE reports should be for a single subject. SAE forms should be sent with a cover sheet and any additional attachments.

All adverse event information is reported to Incyte on MedWatch Form FDA 3500A. The Principal Investigator does not provide medical records (e.g., discharge summary) to Incyte, unless specifically requested.

In addition, all SAEs will be reported to the Prisma Health IRB per the institutional policy for reporting.

Reporting of Pregnancy to Incyte

An "Initial Pregnancy Report" or equivalent must be completed in full and emailed to [contact] or faxed to (+) [name] within 24 hours of discovery of a pregnancy of a subject who has taken the Incyte product or the pregnancy of a partner

for a subject who has taken the Incyte product. The “Follow-up Pregnancy Report Form” or equivalent must be completed and emailed to [contact] or faxed to (+) [name] within 30 days after delivery, so that Incyte is provided with information regarding the outcome of the pregnancy. If the pregnancy results in any events which meet the serious criteria (i.e., miscarriage or termination), the SAE reporting process needs to be followed and the timelines associated with a SAE should be followed.

Statistical Analyses

General Statistical Considerations

Standard statistical methods will be employed to analyze all data. It is anticipated that the following techniques may be used: descriptive statistics, t-test, Chi-square, Fisher’s exact test, Kaplan-Meier analysis, and graphical displays. This protocol may not reflect all analyses planned for the study; additional analyses may be conducted for observational purposes only.

Summary statistics will consist of numbers and percents of responses in each category for discrete measures, and of mean, n, standard deviation, median, minimum, maximum and 95% confidence intervals for continuous measures.

Sample Size Determination

The initial sample size is 20. Each cohort will enroll 10 patients. This number is considered sufficient for an exploratory pilot study to provide information for planning further investigations.

Analysis of Safety

The safety evaluation will compare the proportion of Subjects in each treatment group who exhibit treatment-related adverse effects. These adverse events will be presented for individual patients as a listing of events.

Dissemination of Results

Results of this study may be used for presentations, posters, publications, or extramural grant applications. The publication will not contain any identifiable information that could be linked to a study patient.

References

<https://doi.org/10.1038/s41586-020-2012-7>
2. World Health Organization. Novel coronavirus situation report-2. January 22, 2020.
<https://www.who.int/docs/default-source/coronavirus/situation-reports/20200122-sitrep-2-2019-ncov.pdf> (Accessed on April 7, 2020).
3. P. Conti, G. Ronconi, A. Caraffa, C. Gallenga, R. Ross, I. Frydas, S. Kritas. Induction of pro-inflammatory cytokines (IL-1 and IL-6) and lung inflammation by COVID-19: anti-inflammatory strategies. *J Biol Regul Homeost Agents*. 2020 Mar 14; 34(2).
4. Puja Mehta, Daniel F McAuley, Michael Brown, Emilie Sanchez, Rachel S Tattersall, Jessica J Manson. COVID-19: consider cytokine storm syndromes and immunosuppression. *The Lancet*. 28 March–3 April 2020.

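### Secondary endpoint 1 relates clinical course to the size of the cytokine fall with no stated conditioning on the starting level, which can bias the association and, in some settings, reverse its sign

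*Combined protocol and SAP*

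**What the plan says.** The protocol's Secondary Endpoints, item 1, reads in full: "To correlate the clinical course of participants with the degree of specific cytokine reductions". It gives no scale for the reduction (absolute, percent or log), no reference value, no clinical outcome, no coefficient and no covariate.

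General Statistical Considerations lists techniques that may be used: "descriptive statistics, t-test, Chi-square, Fisher’s exact test, Kaplan-Meier analysis, and graphical displays". No correlation or regression method is among them. The list is left open, since "additional analyses may be conducted for observational purposes only".

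The only decrease that the protocol defines is in the Overall Response Rate (Data Collection, Analysis and Outcomes). It is a 33% or greater "decrease in the cytokine load from peak value through study day 14 in one-third or more participants". It concerns cytokine load rather than specific cytokines, is measured from the peak, and is not tied to this endpoint.

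The population is "COVID-19 positive patients with PENN grade 2, 3, 4 CRS and respiratory failure", so severity varies at entry. Allocation is "Two sequential cohorts, 10 patients per cohort". The Schedule of Assessments and both Appendix B tables include a cytokine panel at screening, before any study treatment, and then daily. GM-CSF is at screening in both tables.

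**The concern.** A fall is the starting level minus a later level, so it is arithmetically coupled to the starting level. A patient who starts high has further to fall. If starting high also goes with being sicker, the correlation between fall and outcome mixes two things: started high, therefore did badly; and fell, therefore did better. These pull in opposite directions.

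The study's rationale is that depleting cytokines helps patients, and the pilot is meant to generate hypotheses. A correlation that shows larger falls going with worse courses, when lower later levels in fact help, would misdirect that next step. Complete 14-day data would not cure this, nor would more patients, because it is bias and not noise.

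There is a second, conditional issue. The cohorts are sequential, so treatment and calendar period move together. If the 20 patients are pooled, a difference between cohorts can pass for a patient-level association.

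**Working it through.** **Inputs from the documents.** "The initial sample size is 20. Each cohort will enroll 10 patients"; 10 + 10 = 20. No alpha, power, effect size or SD is stated, so there is no further plan figure to reproduce.

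**Inputs assumed.** X0 is the log starting level (SD 1). X1 is the log later level (SD k, correlation ρ with X0). D = X0 − X1 is the log fall. Clinical course, higher being worse, is S = aX0 + bX1 + noise (SD 1). With b > 0, a lower later level truly helps. The values of a, b, ρ and k are all assumptions.

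**Step 1: equal variances (k = 1).** cov(D, S) = a(1 − ρ) + b(ρ − 1) = (1 − ρ)(a − b). The raw association points the wrong way when a > b, for any ρ < 1.
- a = 0.6, b = 0.3: 0.7 × 0.3 = +0.21 at ρ = 0.3; 0.5 × 0.3 = +0.15 at ρ = 0.5.
- a = b = 0.3: 0.
- a = 0, b = 0.3: −0.21 and −0.15.
- b = 0 (no true effect): (1 − ρ)a, which is positive whenever a > 0, a false signal of harm.

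**Step 2: size of the bias.** var(D) = 2(1 − ρ), so the raw slope of S on D is (a − b)/2. Rewriting S = (a + b)X0 − bD + noise, the slope of D at a given X0 is −b. The difference is (a − b)/2 + b = (a + b)/2, which is toward harm whenever a > −b. For b = 0.3, the raw slope is +0.15, 0 and −0.15 at a = 0.6, 0.3 and 0, against −0.30 after conditioning.

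**Step 3: simulated trials of n = 20**, raw Spearman against Spearman partial on X0:

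| a | b | k | ρ | Raw, wrong sign | Conditional on X0, wrong sign |
|---|---|---|---|---|---|
| 0.6 | 0.3 | 1 | 0.3-0.5 | 68-71% | 14-19% (all three k = 1 rows) |
| 0.3 | 0.3 | 1 | 0.3-0.5 | 50% | as above |
| 0 | 0.3 | 1 | 0.3-0.5 | 24-28% | as above |
| 0.6 | 0.3 | 1.5 | 0.5 | 25% | 8% |

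**Step 4: unequal variances.** cov(D, S) = a(1 − ρk) − bk(k − ρ). At ρ = 0.5, k = 1.5 this is 0.25a − 1.5b, so reversal needs a > 6b. At a = 0.6, b = 0.3 it is 0.15 − 0.45 = −0.30, the right sign on average. At k = 2 it is 0 × a − 3b, so no positive a reverses it; the raw sign is wrong in 7% of trials.

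**Step 5: choice of scale.** Percent fall is 1 − exp(−D), which rises with D, so it ranks patients as the log fall does and gives the same Spearman value. Absolute fall reverses sooner. With a = b = 0.3, ρ = 0.5 and a mean fall of 1 log unit, percent gives 0.00 and absolute gives +0.21 (wrong sign in 81%). If the log fall is independent of the starting level (SD 0.5), percent does not reverse (−0.13 to −0.11 over the settings with a from 0 to 0.7), while absolute does (+0.19 to +0.56).

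**Step 6: precision.** The 95% interval around r = 0 at n = 20 is ±tanh(1.96/√17) = ±0.44. With two covariates it is ±tanh(1.96/√15) = ±0.47.

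**The case against.** The strongest reply is that the protocol never commits to an unadjusted analysis. The endpoint is one line, the method list is open, and a start-minus-later difference and a pooled correlation are readings supplied from outside. That stands in part: the omission is by silence. But the stated predictor is the reduction itself, and no section brings in the starting level.

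A second reply is that reversal depends on chosen values. This also stands. The raw sign is right on average when a < b, and usually when later levels vary much more than starting levels. If clinical course means improvement from entry, a could be small or negative. At a = −b the bias is zero and conditioning gains nothing: with a = −0.3, b = 0.3 and ρ from 0.3 to 0.7, the raw log or percent correlation is wrong in 8-18% of trials and the adjusted one in 13-19%. In the settings with a of 0 or more and a true effect, the adjusted estimate had fewer wrong signs.

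A third reply is that n = 20 over six cytokines cannot settle a sign anyway. Imprecision is real, but it is no reason to keep a removable bias.

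Three stronger readings are tempting and not supported:
- A reader might infer that the analysis will return the wrong sign. The documents contain no cytokine levels by grade, so only the possibility is shown.
- A reader might infer that this is the only link from cytokines to outcome, or the main input to later work. Secondary item 6 allows exploratory biomarker work, and the protocol does not rank its endpoints for that purpose.
- A reader might infer that the planned methods rule out adjustment. The list is expressly not exhaustive.

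**Conclusion.** The point holds as a possible bias in a secondary, exploratory endpoint. As written, the endpoint uses the fall as predictor without the level it fell from. If starting level tracks severity, the unadjusted correlation leans toward making reduction look unhelpful, by (a + b)/2 on the slope scale under equal variances, and reverses when a > b. Within the assumed range the wrong-sign share runs from about a quarter to about 70% unadjusted, against about 14-19% adjusted. With an SD ratio of 1.5 the contrast is 25% against 8%.

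These figures rest wholly on assumed weights, correlations and SDs. What does not rest on them is that a reduction contains the starting value and that a pre-treatment value is already collected, so a better-conditioned analysis is available at almost no cost. The primary endpoints are not affected by this point. It is worth correcting before the data are analysed.

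**What to change.** Add one paragraph to Statistical Analyses for secondary endpoint 1:
- Name one clinical outcome and one fixed study day. Day 14 is sampled in both cohorts and is not an exchange day, so there is no choice between pre- and post-procedure samples. State how patients with no sample that day, including deaths, are handled.
- For each cytokine, report the association of that outcome with the log level on that day (or the log change to it), conditional on the patient's own pre-treatment log level, and on cohort if the cohorts are pooled.
- Use a partial Spearman correlation or rank regression with a 95% CI, and label it descriptive.
- Do not present unadjusted reduction-outcome correlations as evidence that lowering cytokines helps.

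Cost: no new samples, since the screening panel is scheduled in both cohorts, and about 2 degrees of freedom of 20. Limits: intervals stay wide (Step 6), and conditioning removes the coupling with the starting level but not all confounding by severity or by cohort and period.

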
 • Access Central Venous Catheter 	Daily

 • Access A/V Fistula for Procedure 	Daily
Pre-Procedure Labs (Baseline)	

 • CBC with Differential 	Once

 • CMP 	Once

 • Fibrinogen 	Once
Anticoagulant Prime	

 • Anticoagulant citrate dextrose injection 500 ml 	PRN
Medications	

 • calcium carbonate tablet 1000 mg PO 	PRN

 • calcium gluconate 2.5g in NS 250ml IV 	PRN

 • alteplase 2mg in 10ml syringe 	PRN clot clearance
Hypersensitivity Regimen	

 • at any sign of anaphylaxis, stop infusion, notify MD and administered prescribed medications 	PRN

 • diphenhydramine (Benadryl) 50 mg IV 	PRN

 • methyleprednisolone (Solu-Medrol) 40 mg IV 	PRN

 • famotidine (Pepcid) 20 mg IV 	PRN
Nursing Orders	

 • Infuse Albumin 	Once

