Appendix B: COHORT 1B Schedule of Assessments: Therapeutic Plasma Exchange Plus Ruxolitinib																	
Assessment	Screening (24 hours)	Study Day															
		0	1	2	3	4	5	6	7	8	9	10	11	12	13	14	28
Informed Consent and Medical History	X																
Physical Examination ^a	X	X	X	X	X	X	X	X	X	X	X	X	X	X	X	X	X
Complete Blood Count (CBC)	X	X	X	X	X	X	X	X	X	X	X	X	X	X	X	X	X
Comprehensive Metabolic Panel (CMP)	X																
Basic Metabolic Panel (BMP)		X	X	X	X	X	X	X	X	X	X	X	X	X	X	X	X
C-Reactive Protein (CRP)	X	X	X	X	X	X	X	X	X	X	X	X	X	X	X	X	X
Ferritin	X			X				X			X					X	
Hepatitis Serology ^b	X																
Lipid Panel ^b	X																
PT/INR	X																
PTT	X																
Fibrinogen	X		X	X		X		X		X		X					
Type and Screen ^b	X																
Serum Pregnancy Test ^b	X																
Cytokine Panel (IL-6, IL-8, IL-10, TNF α , IFN γ) ^c	X	X	X	X	X	X	X	X	X	X	X	X	X	X	X	X	X
GM-CSF ^c	X	X	X	X	X	X	X	X	X	X	X	X	X	X	X	X	X
Peripheral Blood for biorepository	X					X				X							X
Peripheral Blood for pharmacogenomics	X																
PaO ₂ /FiO ₂ ratios (with ABGs) - (mechanically vented patients only)		X		X		X											
Supplemental O ₂ , SPO ₂ %, Respiratory Rate, Imaging at MD discretion (for NON-intubated patients)		X	X	X	X	X	X	X	X	X	X	X	X	X	X	X	X
SPO ₂ %, FiO ₂ , PEEP, Lung compliance (inspiratory pause - Vt/Pplat-PEEP) or plateau pressures (mechanically vented patients only)		X	X	X	X	X	X	X	X	X	X	X	X	X	X	X	X
Therapeutic Plasma Exchange (TPE) (plus waste for biorepository)			X	X		X		X		X							
Ruxolitinib Dosing		X	X	X	X	X	X	X	X	X	X	X	X	X	X	X	X

^a If patient is discharged from the hospital, daily physical examination will not be required. Perform one physical exam prior to the patient's last study visit. Day 28 may be a virtual visit if needed.

^b Hepatitis serology, Lipid panel, Type and Screen, Serum Pregnancy Test acceptable within 7 days prior to enrollment.

^c Cytokine Panel and GM-CSF are to be repeated within 60 minutes post TPE on days of plasma exchange procedure only.

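### The ruxolitinib AST/ALT dose-reduction rule has no assured laboratory input on dosing days 9–13

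*Combined protocol and SAP*

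**What the plan says.** In the combined protocol and SAP, the Dose Modifications section sets the rule: "AST/ALT > 5x ULN, reduce dose of ruxolitinib to 5mg po once daily". It also sets how often the rule is applied: "The need for dose adjustments will be assessed on a daily basis by the research team and pharmacist".

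The Treatment Plan for cohort 1B gives "ruxolitinib 5mg po BID beginning day prior to first TPE and continuing BID for total of 14 days". Counting the day before the first exchange as day 0, as Appendix B does, dosing covers days 0–13.

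The Schedule of Assessments lists a CMP among the pre-treatment tests. Its on-study list has a "daily Basic Metabolic Panel (BMP") and no CMP, AST, ALT or liver panel. The cohort 1B table in Appendix B agrees: the CMP row has a single mark, under the 24-hour screening column, and the BMP row is marked every day from day 0. The exchanges are marked on days 1, 2, 4, 6 and 8.

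The exchanges are given "with albumin or FFP replacement if underlying coagulopathy per institutional protocol (Appendix A"). Appendix A holds two order sets. The albumin plan lists a CMP *Once* under its pre-procedure baseline labs and has no daily labs. The plasma plan lists a CMP *Once* under the same heading and again *Daily*, with no stop day.

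**The concern.** A rule that is to be applied daily needs a current value. The platelet and creatinine clearance rules can draw on the daily CBC and BMP. The AST/ALT rule has no matching entry in the study schedule after screening, so a site that follows the schedule exactly can dose on days when the rule cannot operate.

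Three features raise the stakes for the up to 10 patients in cohort 1B:

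- Exclusion 14 admits patients with AST/ALT up to 5 times the upper limit of normal, which is the trigger level. A patient near that limit has no margin.
- The Risk Analysis lets patients who improve go home once the exchanges are finished. Their daily outpatient follow-up is tied to the assessments the study requires, and those carry the BMP.
- Therapy-related adverse events are a primary endpoint, graded by CTCAE. A transaminase rise that is not measured cannot be graded.

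**Working it through.** **Panel contents (assumption).** The protocol does not say what its panels contain. By usual contents a CMP includes AST and ALT and a BMP does not. The protocol is consistent with this: it lists the two as different tests, and among the pre-treatment tests the CMP is the only one that could supply the AST/ALT needed for exclusion 14.

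**Dosing days.** 14 days starting on day 0 gives days 0–13. The ruxolitinib row in Appendix B, as extracted, carries 16 marks running to the day 28 column, so I count from the Treatment Plan text. If day 14 were also a dosing day, the gap below would be one day longer. The 24-hour screening CMP informs day 0.

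**Coverage of days 1–13 under each reading of the orders.**

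| Reading | Days with AST/ALT ordered | Days without | Age of last value on day 13 |
|---|---|---|---|
| Study schedule alone | none | 1–13 | screening value only |
| Albumin plan, CMP at each exchange | 1, 2, 4, 6, 8 | 3, 5, 7 and 9–13 | 13 − 8 = 5 days |
| Albumin plan, CMP once per course (day 1) | 1 | 2–13 | 13 − 1 = 12 days |
| Plasma plan, daily until the last exchange | 1–8 | 9–13 | 13 − 8 = 5 days |
| Plasma plan, daily continued to the last dose | 1–13 | none | 0 days |

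For the albumin plan, the per-exchange reading is the more likely one. The orders to infuse albumin and to transfuse plasma are also marked *Once*, and each must happen at every exchange. The heading "Pre-Procedure Labs (Baseline") leaves the per-course reading open. On the per-exchange reading, days 3, 5 and 7 rely on a value one day old, which is a small matter. Days 9–13 are five consecutive dosing days with no draw.

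**Size.**

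- Share of dosing days: 5 / 14 = 36%.
- Doses given in that window: 5 days × 2 = 10 per patient.
- Upper bound over cohort 1B, if all 10 patients are albumin-replaced and complete dosing: 10 × 5 = 50 of 10 × 14 = 140 patient-days.
- Missed reduction, if the trigger is crossed just after the day 8 draw: 10 doses × 5 mg = 50 mg given, against 5 doses × 5 mg = 25 mg under the rule. The excess is 25 mg per patient.

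The documents give no rate of AST/ALT rise, so the chance of a missed trigger cannot be calculated.

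**The case against.** The strongest reply is that the schedule is a floor and not a ceiling. Ruxolitinib is to be used according to its package insert, the AST/ALT rule cites that insert, both cohorts receive standard medical care, and the daily review by team and pharmacist arguably obliges them to obtain the value. This has some force: a clinician may well order liver tests, and the insert cannot be checked here. But none of these provisions states an AST/ALT test, and the protocol's own list of on-study standard care names the BMP. The accurate wording is that the test is not assured, and that is the claim made.

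Second, Appendix A is part of the treatment plan, and its plasma plan may continue a daily CMP without limit. That reading leaves no gap for plasma-replaced patients and is shown above. It does not help albumin-replaced patients.

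Third, the 50 patient-days and the 25 mg are upper bounds. That is correct; neither is an expected value.

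Fourth, the neutrophil rule may have a similar weakness, because the study schedule says CBC while Appendix A specifies a differential. Panel names could therefore be shorthand. No claim is made here about neutrophils, and the distinction the protocol draws between CMP and BMP is explicit.

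Fifth, a daily panel in both cohorts may be more than is needed, since a few AST/ALT checks in cohort 1B on days 9–13 would break the gap. Sparser testing could be defended if the protocol also stated an interval for this rule. As written, the rule is applied daily and blood is already drawn daily.

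**Conclusion.** The concern holds and should be fixed. The study schedule orders no AST/ALT after screening. With full credit for Appendix A, none is ordered on days 9–13 for albumin-replaced patients and none is assured for plasma-replaced patients. The conclusion rests on usual panel contents, on dosing days counted from the Treatment Plan text, and, for the length of the gap, on the per-exchange reading of the albumin plan. The per-course reading makes the gap longer.

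The consequence is limited: at most 10 patients, late in treatment, and a halving of the dose that might be missed. Sample size and error rates are unaffected. No bias in the safety comparison between cohorts is claimed, because both have the same CMP/BMP pattern and the same Appendix A.

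**What to change.** In the on-study list of the Schedule of Assessments and in Appendix B, replace the daily BMP with a CMP, or add AST/ALT to the same draw. In cohort 1B this should run through the last ruxolitinib dose (days 0–13), including outpatient days after discharge. Use the same panel in cohort 1A on days 1–13, where the 24-hour screening CMP stands for day 0. Matching matters because the Analysis of Safety section compares treatment-related adverse effects between the groups, and daily liver tests in cohort 1B alone would make hepatic events easier to find there. The dose thresholds stay as they are.

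The cost is an edit to one bullet and to the CMP and BMP rows of two tables, with no additional blood draw. The laboratory cost is at most 10 × 14 = 140 upgraded panels in cohort 1B plus 10 × 13 = 130 in cohort 1A, or 270 in total, and fewer where Appendix A already orders a CMP.
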